#### **5.6 Prohibited Medications/Treatments**

Investigators will contact Imago staff with any questions pertaining to prohibited medications.

1. All cytotoxic agents, including standard-of-care therapies for ET

2. All hematopoietic growth factors: romiplostim, eltrombopag, erythropoietin (EPO), granulocyte colony stimulating factor (G-CSF) and granulocyte-macrophage colony stimulating factor (GM-CSF)
3. Monoamine oxidase A and B inhibitors
4. Anticoagulant and nonsteroidal anti-inflammatory drug (NSAID; including aspirin) use are prohibited in patients when their platelet count is  $< 50 \times 10^9/\text{L}$  ( $50,000/\mu\text{L}$ )

## 6 Study Treatment

IMG-7289, is an irreversible inhibitor of the enzyme LSD1 being developed by Imago BioSciences, Inc. For pre-clinical, clinical and formulation information see the most recent Investigator's Brochure (IB) for IMG-7289.

The drug product is IMG-7289, a bis-tosylate salt. The free base of IMG-7289 is the active moiety. IMG-7289 will be supplied to the site pharmacy department by Imago BioSciences (or designee) in bottles containing capsules in accordance with all applicable regulatory requirements. The capsule strengths to be provided, based on IMG-7289 free base, i.e., the active substance, may include: 5 mg, 10 mg, 25 mg, and 50 mg. Additional strengths may be added over the duration of the study. Such details will be included via updates to ancillary study documents and not the study protocol.

The capsules will be manufactured in accordance with Annex 13 and principles of cGMP at:

Xcelience LLC  
[name]  
[name]

Upon supply to site, labels will be in accordance with all applicable regulatory requirements for the labeling of active pharmaceutical ingredients and with Annex 13 of GMP.

The recommended long-term storage conditions for IMG-7289 is for the storage temperature not to exceed 25°C. IMG-7289 must be stored in a secure area with access limited to the Investigator and authorized staff and under the physical conditions that are consistent with IMG-7289-specific requirements.

### 6.1 Dosing and Administration

Participants will be initiated on a daily oral dose of 0.6 mg/kg/day of IMG-7289. Dose escalation and de-escalation rules are detailed below targeting a platelet count of 200 to  $400 \times 10^9/\text{L}$  and a hemoglobin of 10-13 g/dL via hematology evaluations (evaluations are weekly for the first 8 weeks, bi-weekly for the next 8 weeks, and then monthly). **Up-titration**s may begin on ITP Day 29 and occur no more frequently than every 4 weeks from the previous up- or down-titration. **Down-titration**s can be made at any time in the best interest of the patient.

Trained personnel will provide instruction pertaining to IMG-7289 administration and supervise the administration of IMG-7289 on any day that it is taken in the clinic. With the exception of ITP Day 1 it is not required that IMG-7289 be taken in the clinic; this will be determined based on the patient's regular daily dosing time. When applicable, the date and time of each administration in the clinic will be recorded in the source notes.

IMG-7289 dosing will be based on the patient's ITP Day 1 weight. If during the study, the patient's weight differs from ITP Day 1 by more than 10%, the amount of IMG-7289 dispensed should be corrected per the dose chart provided. In cases where using the ITP Day 1 weight is impractical for dispensing, a weight taken as close to ITP Day 1 as possible (e.g., Screening) may be used; weight at a current visit may also occasionally need to be used. The source data must clearly document the weight used.

Patients will be provided supply of IMG-7289 capsules at the time of their visits throughout the study (weekly for the first 8 weeks, followed by monthly). There is no additional preparation required.

Patients should be instructed to:

- Take their IMG-7289 orally once daily, at approximately the same time
- When possible, take IMG-7289 on an empty stomach (fast for 1 hour prior to and 30 minutes after dose). If needed, and at the discretion of the PI, IMG-7289 may be taken with food.
- Swallow their IMG-7289 capsules whole, with an 8oz glass of water

Patients may have clear liquids prior to and after the fasting periods have been completed.

## 6.2 Dosage: Initial Treatment Period

In the Initial Treatment Period, all patients will be treated daily, for up to 169 days of dosing. Dosing will begin on Day 1 at the starting dose, 0.6 mg/kg/d IMG-7289 free base. Details on the selection of and rationale for the starting dose and dosing schedule can be found in Section 3.4 and Section 3.5.

Through the use of dose titration, all patients will be dosed to the  $D_{pi}$ ; the dose needed to safely inhibit normal hematopoiesis for a fraction of the dosing cycle. Dose-titration, both upward and downward, is contingent on the hematology assessment and comparison of hematology values from the prior visit.

**Up-titration**s may begin on ITP Day 29 and occur no more frequently than every 4 weeks from the previous up- or down-titration. **Down-titration**s can be made at any time in the best interest of the patient.

The  $D_{pi}$  is anticipated to be approximately 2 mg/kg QD; however, this is not the upper limit for titration purposes as the dose needed to achieve a therapeutic effect will vary among patients and may change over time. The platelet titration target expected to be associated with a clinically significant therapeutic effect is:

- A platelet count of  $\geq 200$  to  $\leq 400$   $\text{k}/\mu\text{L}$  ( $200-400 \times 10^9/\text{L}$ )

Titration and re-challenge rules based on periodic evaluation of platelet, absolute neutrophil (ANC) and hemoglobin (Hb) counts are noted below.

**Table 1: Titration and Re-challenge Rules**

Titration and Re-challenge Rules				
Hematology Assessment		Titration and Re-challenge Rules		
Plt Count ( $\times 10^9/\text{L}$ )	Hb Level (g/dL)	Titration?*	Titration Rule*	Re-challenge Rule*
$> 400$	$\geq 10$	Up-titrate □	Increase by 0.2 mg/kg/d □	N/A
$\geq 200$ to $\leq 400$	$\geq 10$	Maintain current dose	N/A	N/A
50-199	$\geq 10$	Down-titrate	Decrease by 0.1 mg/kg/d	N/A
N/A	8.5 to <10	Down-titrate	Decrease by 0.15 mg/kg/d	N/A
< 50	< 8.5	HOLD DOSE □	N/A	At 50% of prior dose** when: - platelets return to $\geq 100$ - Hb returns to $\geq 8$ ***

□Up-titration may begin on ITP Day 29 and occur no more frequently than every 4 weeks from the previous up- or down-titration. Down-titration can be made at any time in the best interest of the patient.

\*Patients requiring a dose hold should have complete blood counts monitored at least weekly for safety purposes and to enable re-challenge to commence as soon as counts return to the required level, if safe to do so.

\*\*The PI may, upon review of individual patients and patient responses, recommend up- or down-titration that are not in concordance with the above.

\*\* Re-challenge at 50% of the previous mg/kg dose.

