- Any Grade 3 or above non-hematologic adverse event with the following exceptions:
  - Nausea, vomiting or diarrhea lasting 3 days or less
  - Aesthenia lasting less than 7 days
- Any Grade 3 electrolyte abnormality unrelated to the underlying malignancy and persisting greater than 24 hours.

\*A clinically significant bleeding event is defined as an event that is life-threatening, cannot be controlled and/or results in hemodynamic instability.

Patients who experience a DLT may have their dose adjusted downward if the Sponsor Investigator (PI) deems it safe for the patient to continue on IMG-7289. Any patient that experiences DLT that results in discontinuation of IMG-7289 therapy may begin alternative cytoreductive therapy to lower platelets within 24-48 hours.

The SI will contact Imago medical staff to discuss IMG-7289 dose modifications for the management of clinically significant changes in platelets, neutrophil counts, or other hematologic parameters.

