**Stopping Rules:**

IMG-7289 will be discontinued in the event of the following:

- Post DLT, the Principal Investigator deem it unsafe for the patient to continue on IMG-7289.
- Post dose reduction due to DLT, the patient either worsens at any time or fails to demonstrate significant improvement within 14 days.
- Post temporary interruption of IMG-7289 due to platelet counts below  $50 \times 10^9/L$  (50,000/ $\mu L$ ), the patient's platelet counts don't return to  $> 150 \times 10^9/L$  (150,000/ $\mu L$ ) within 21 days.
- Any Grade 4 non-hematologic adverse event with failure to recover to Grade 3 within 7 days of drug cessation.

**Study Design:** This study will follow a Simon two-stage design with an anticipated lower limit response rate of 10% and a target response rate of >40%. With these parameters, the optimal Simon design with  $\alpha=0.05$  and 90% power would need 9 patients in the first stage and 11 patients in the second stage. After testing oral IMG-7289 on 9 patients in the first stage, the trial will be terminated if 1 or fewer respond. If the trial goes to the second stage, a total of 20 patients will be enrolled. If the total number responding is less than or equal to 4, oral IMG-7289 will be rejected; if the total number responding is more than 4, oral IMG-7289 will be considered worthy of further study.

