### **5.4 Inclusion and Exclusion Criteria**

#### **5.4.1 Inclusion Criteria**

Inclusion criteria are as follows:

1. Age  $\geq 18$  years.
2. Diagnosis of Essential Thrombocythemia per World Health Organization (WHO) diagnostic criteria for myeloproliferative neoplasms ([Arber et al., 2016](#)).
3. Patients who are intolerant or resistant to hydroxyurea per ELN criteria, or in the Investigator's judgment are not candidates for available approved therapy. The ELN definitions of resistance/intolerance to HU requires the fulfillment of at least one of the following criteria:
  - Platelet count  $>600 \times 10^9$ /L after a daily dose of at least 2 g HU for at least 3 months (2.5 g/day in patients with a body weight over 80 kg);
  - Platelet count  $>400 \times 10^9$ /L and WBC  $<2.5 \times 10^9$ /L at any dose of HU;
  - Platelet count  $>400 \times 10^9$ /L and hemoglobin  $<10$ g/dL at any dose of HU
  - Presence of unacceptable HU-related non-hematologic toxicities, including fever, mucocutaneous manifestations or leg ulcers.
4. Requires treatment in order to lower platelet counts based on the Clinically Relevant IPSET-Thrombosis Guidelines.
5. Platelet count  $>450 \times 10^9$ /L pre-dose Day 1.
6. Peripheral blast count  $\leq 5\%$  pre-dose Day 1.
7. ANC  $\geq 0.5 \times 10^9$ /L pre-dose Day 1.
8. Fibrosis Score  $<$ grade 2, as per a slightly modified version ([Arber et al., 2016](#)) of the European Consensus Criteria for Grading Myelofibrosis, ([Thiele et al., 2005](#)).

9. Life expectancy > 36 weeks.
10. Able to swallow capsules.
11. Amenable to spleen size determination, bone marrow evaluations (in the ITP only, optional in the ATPs), and peripheral blood sampling during the study.
12. Must have discontinued ET therapy at least 2 weeks (4 weeks for interferon) prior to study drug initiation.
13. Agrees to use an approved method of contraception from Screening until 28 days after last administration of the study drug. Acceptable methods of birth control include: birth control pills, depo-progesterone injections, a vaginal hormonal contraceptive ring, a barrier contraceptive such as a condom with spermicide cream or gel, diaphragms or cervical cap with spermicide cream or gel, or an intrauterine device (IUD).
14. If male, agrees not to donate sperm or father a child for at least one month after the last dose of the study medication.

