## Titration and Re-challenge Rules

\*\*\*PRBC transfusions allowed if at 0.15 mg/kg/d down-titrated dose level transfusions requirement remains stable within 2 units per month, and no more than 4 units total per 28 days, and patient otherwise has evidence of clinical benefit.

\* Upon re-challenge, all of the above rules reapply.

Please consult the Principal Investigator regarding dose modifications of IMG-7289 should an adverse event (AE) requiring a dose reduction occur, and also for the management of clinically significant changes in platelets, neutrophil counts, or other hematologic parameters.

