patient-derived malignant myeloid cells as well as *JAK2V617F* cell lines are similar to concentrations that *in vivo* inhibit red cell, platelet and granulocyte production. It is therefore expected that ET patients will require treatment at doses sufficient to reduce platelet counts and hemoglobin counts, respectively, and, to a lesser degree, absolute neutrophil counts. These reversible cytopenias can be managed clinically as needed with transfusions as well as broad-spectrum antibiotics in the case of febrile neutropenia as are already standard practices in the routine management of malignant myeloid diseases.

The effects of IMG-7289 on normal myeloid hematopoiesis observed in non-clinical studies are expected in humans; these are pharmacodynamic effects of LSD1 inhibition by IMG-7289, thus are not regarded as adverse. These events, with the exceptions below, will not be considered DLTs.

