### 6.5.4 Interruption of Dosing

Patients requiring a Dose Hold according to the Titration and Rechallenge Rules, or due to an (S)AE, should be monitored at least weekly for safety purposes and to enable re-challenge to commence as soon as counts

return to the required level, if it safe to do so. During these visits, patients are required to undergo complete blood counts only.

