#### Reporting Requirements

For this study, the Master Adverse Events Documents collected on patients for this protocol will be reviewed by the Principal Investigator on a continuous basis to determine if a serious safety problem has emerged that result in a change or early termination of a protocol such as:

- suspending enrollment due to safety or efficacy, or
- termination of the study due to a significant change in risks or benefits.

The PI will provide the DSMB with the quarterly findings for discussion and review during their meetings.

The PI (or designee) is responsible for notifying sub-investigators regarding recommendations to modify the dosage (dose escalate, dose decrease – outside of the per patient defined titration plan) to ensure that subsequent subjects are treated at the currently approved dose level. As per the protocol, the PI will contact Imago medical staff to discuss protocol modifications for the management of clinically significant changes in platelets, neutrophil counts, or other hematologic parameters. Discussions with Imago staff will be documented and decisions shared with the DSMB and all sub-investigators. In the event starting doses are modified, the PI may delegate the study coordinator to notify other Mays staff, including the Investigational Drug Section to ensure that orders are modified timely and appropriately.

Additionally, this study will have an interim analysis after the first 9 patients to review for response rate. The results of the first 9 patients should be shared with the DSMB to approve extending the study to an additional 11 subjects. The PI is responsible to for notifying sub-investigators of the hold on enrollment until the DSMB has recommended continuance of the study.

Stopping rules for this study include 2 DLT's in the first cohort of 9. A DLT is defined as any one of the following AEs that occurs through Day 7 of the Initial Treatment Period unless the event is considered by the Investigator to be clearly unrelated to IMG-7289:

- Any Grade 3 or above thrombocytopenia associated with clinically significant bleeding\*;
- Any Grade 4 thrombocytopenia associated with the requirement for platelet transfusion;
- Any Grade 4 or 5 non-hematologic adverse event;
- Any Grade 3 or above non-hematologic adverse event with the following exceptions:
  - Nausea, vomiting or diarrhea lasting 3 days or less

- Aesthesia lasting less than 7 days

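### Table 1 does not reliably order a dose hold at platelets below 50 × 10⁹/L when hemoglobin is 8.5 to <10 g/dL

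*Combined protocol and SAP*

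**What the plan says.** Table 1 in section 6.2, and its copy in the synopsis under IMG-7289 Dosing, has five rows keyed to platelets (× 10⁹/L) and hemoglobin (g/dL).

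- The first three rows each pair a platelet band (>400, 200 to 400, 50 to 199) with hemoglobin ≥10. They order an increase of 0.2 mg/kg/d, no change, and a decrease of 0.1 mg/kg/d.
- The fourth row, hemoglobin 8.5 to <10, has N/A for platelets and orders "Decrease by 0.15 mg/kg/d".
- The fifth row lists platelets <50 and hemoglobin <8.5, with no connecting word, and orders a hold. Re-challenge is at half the prior dose once platelets reach 100 and hemoglobin reaches 8.

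Section 6.5.3, like the synopsis Stopping Rules, requires discontinuation in this case: "Post temporary interruption of IMG-7289 due to platelet counts below" 50 × 10⁹/L, with no return to above 150 within 21 days. No hemoglobin condition is attached.

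For any patient on a hold, section 6.5.4 says that they "should be monitored at least weekly for safety purposes".

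The notes to Table 1 let the Principal Investigator depart from the table and direct staff to consult the Principal Investigator "for the management of clinically significant changes in platelets, neutrophil counts, or other hematologic parameters".

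**The concern.** N/A in the platelet column means that the anemia row applies at any platelet count, including below 50. At that level the rest of the protocol assumes that drug is stopped: section 6.5.3 speaks of an interruption, and section 5.6 prohibits anticoagulants and NSAIDs. Yet the anemia row keeps the patient on drug at a modest reduction. Nothing in the table notes or in sections 6.3, 6.5.3 or 6.5.4 says which row governs when two could apply.

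What is at stake is patient safety in one narrow situation. Two safeguards are triggered by a hold: the weekly blood count and the 21-day recovery stop. If staff follow the anemia row, no hold is in force and neither safeguard starts.

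**Working it through.** **1. Orders under each reading of the hold row.** Crossing four platelet bands with three hemoglobin bands gives 12 combinations. The table does not print the connecting word, so both readings are checked.

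| Platelets | Hemoglobin | Hold row read as OR | Hold row read as AND |
|---|---|---|---|
| <50 | <8.5 | hold | hold |
| <50 | 8.5 to <10 | reduce 0.15 **and** hold | reduce 0.15 only |
| <50 | ≥10 | hold | no order |
| each of three bands ≥50 | <8.5 | hold | no order |
| each of three bands ≥50 | 8.5 to <10 | reduce 0.15 | reduce 0.15 |
| 50–199 | ≥10 | reduce 0.1 | reduce 0.1 |
| 200–400 | ≥10 | no change | no change |
| >400 | ≥10 | increase 0.2 | increase 0.2 |

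- OR: 11 combinations have one order and 1 has two.
- AND: 8 have one order and 1 + 3 = 4 have none.

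Platelets <50 with hemoglobin 8.5 to <10 is handled badly either way.

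**2. Which reading the protocol supports.** Section 6.5.3 attributes an interruption to platelets alone, so the platelet condition must be able to trigger a hold by itself. That rules against AND, although the first three rows do pair their conditions. Section 6.5.3 is silent on hemoglobin. That hemoglobin <8.5 alone also means hold is the sensible reading, because otherwise three combinations have no order, but it is an inference from the table.

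**3. Dose consequence.** For a current dose d, the anemia row leaves d − 0.15. The hold row leaves 0, then 0.5d on re-challenge.

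| d (mg/kg/d) | Anemia row | Share of d | Hold row | Re-challenge |
|---|---|---|---|---|
| 0.45 | 0.30 | 67% | 0 | 0.225 |
| 0.50 | 0.35 | 70% | 0 | 0.25 |
| 0.60 | 0.45 | 75% | 0 | 0.30 |
| 0.80 | 0.65 | 81% | 0 | 0.40 |
| 1.00 | 0.85 | 85% | 0 | 0.50 |
| 2.00 | 1.85 | 93% | 0 | 1.00 |

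The starting dose is 0.60. One earlier reduction from it gives 0.50 or 0.45. Section 3.4 reports that most myelofibrosis patients needed 0.6 to 0.8. Section 6.2 anticipates about 2 in ET. Within the Initial Treatment Period the rules allow at most 0.6 + 5 × 0.2 = 1.6 (steps on Days 29, 57, 85, 113 and 141). The documents do not say what dose a patient in this situation would be on, so the rows are illustrations.

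Break-even: d − 0.15 = 0.5d gives d = 0.30. Above 0.30 mg/kg/d, the anemia row gives more drug at platelets <50 than the hold row allows after recovery to 100.

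**4. Monitoring consequence.** Scheduled blood counts are 7 days apart to Day 57, 14 days to Day 113, and 28 days afterwards and in the Additional Treatment Period. A hold requires 7. Nothing is lost through Day 57. After that, the gap could be 14 or 28 days. These are worst cases, because section 7 and sections 7.3.3, 7.3.4 and 7.4.2 allow extra visits. The 21-day stop fails to start whatever the visit.

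**The case against.** The strongest reply is that section 6.5.3 settles the matter. If platelets <50 alone mean interruption, staff already know to hold, and the hold row's capital letters and its own monitoring duty point the same way. Most clinicians would probably hold. This is a single-site trial in which staff are told to consult the Principal Investigator. The synopsis adds contact with the manufacturer's medical staff on "dose modifications for the management of clinically significant changes in platelets", and section 11 has the Principal Investigator contact them "to discuss protocol modifications for the management of clinically significant changes in platelets". All of this stands as mitigation. But section 6.5.3 says what follows an interruption; it does not order one or rank the rows. Consultation and discretion supply no default.

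The situation also looks uncommon. Entry requires platelets above 450, so reaching <50 is a fall of at least 1 − 50/450 = 89%, with reductions ordered on the way down. It is not excluded: section 5.4 sets no hemoglobin minimum, and section 6.5.1 says "It is therefore expected that ET patients will require treatment at doses sufficient to reduce platelet counts and hemoglobin counts". The documents give no frequency.

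Three stronger inferences are tempting, and the documents do not support them:

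- **That the table plainly issues two conflicting orders, with every other combination clean.** That needs an 'or' that is not printed. Under AND there is one order, the wrong one, and four other combinations have none.
- **That the stopping rules establish both halves of the 'or'.** They mention platelets only.
- **That the hydroxyurea criterion of hemoglobin <10 shows patients enter anemic.** It describes hemoglobin "at any dose of HU", and ET therapy must stop at least 2 weeks before study drug. It does not establish hemoglobin on study.

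**Conclusion.** The point holds as a defect in a safety rule, and it does not depend on how the hold row is read. At platelets <50 with hemoglobin 8.5 to <10, the OR reading gives two orders without precedence. The AND reading gives a reduction with no hold, at odds with section 6.5.3. The double order rests on the OR reading; the failure to order a hold reliably does not.

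The effect is confined to patients in this combination whose staff follow the anemia row. For them, 67% to 93% of the dose continues over the illustrative range of 0.45 to 2.0 mg/kg/d, and the hold-linked safeguards do not begin. The conclusion assumes only that N/A means any platelet count. It has no bearing on the Simon design, its error rates or the response endpoint. It is minor, but worth correcting because the remedy is so small.

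**What to change.** In both copies of the table (synopsis and section 6.2):

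- change the anemia row's platelet entry from N/A to ≥50;
- word the hold row as platelets <50 **or** hemoglobin <8.5.

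The 12 combinations then each carry one titration order: three at platelets <50 (hold), three at platelets ≥50 with hemoglobin <8.5 (hold), three with hemoglobin 8.5 to <10 (reduce 0.15), and three with hemoglobin ≥10 (the first three rows). A separate precedence sentence becomes optional. The sponsor should confirm that hemoglobin <8.5 alone is meant to trigger a hold.

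The edit does not settle two mismatches, which can be considered in the same amendment. Re-challenge is allowed at hemoglobin ≥8 although the hold applies below 8.5, and at platelets ≥100 although the recovery stop looks for more than 150.

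The cost is one table entry and one row's wording, in two places. Sample size, visits and assessments do not change.

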#### **5.5 Guidelines**

These guidelines are for use by the Investigator, study staff and patient to safeguard patient safety while maintaining data integrity.

1. In general, supportive care (transfusions, administration of anti-fungals, etc.) should be maintained in accordance with institutional policy. Additionally:
  - a. It is advised that patients with a platelet count  $\leq 10 \times 10^9/L$  (10,000/ $\mu$ L) be transfused.
2. Patients taking medications that have the potential to induce or inhibit CYP3A4 or CYP2D6 should be monitored closely for potential effects of co-administration; particular attention should be given to anti-infectives in the azole class.
3. Cessation of IMG-7289 is invariably associated with a rebound in thrombopoiesis and platelet counts may easily exceed the baseline value. When IMG-7289 is discontinued, the platelet count should be monitored closely and an alternative cytoreductive therapy to lower platelets should commence within 24-48 hours.

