#### 6.5.1 Hematologic Toxicities

Hematologic values outside of the normal reference range are inherent features of MPNs and are expected effects of many therapeutic attempts to manage these diseases.

Both genetic knockdown (KD) of LSD1 mRNA and pharmacologic inhibition of LSD1 show that the loss of LSD1 activity arrests the production of mature red cells, platelets and granulocytes while over-producing monocytes ([Sprussel et al., 2012](#); [Kerenyi et al., 2013](#)). Production of cells of lymphoid lineage, B and T cells is unimpaired indicating that LSD1 has very cell-specific functions and its inhibition also has very specific effects. LSD1 inhibition in malignant myeloid cells causes the induction of monocytic differentiation markers, as well as a reduction of self-renewal potential of neoplastic cells, all of which eventually result in apoptosis of treated cells. Thus, the anemia, thrombocytopenia, neutropenia and monocytosis attending LSD1 inhibition, as observed in animals treated with IMG-7289, reflect primary pharmacodynamic effects. The kinetics of anemia, thrombocytopenia, and neutropenia following complete LSD1 inhibition are a function of the lifespan of the individually affected cell types. Over the course of LSD1 inhibition, platelet and neutrophil counts are the most affected, reflecting their short mean lifespans of approximately seven and twelve days, respectively. Recovery of peripheral counts is reversible, rapid, and temporarily overshoots baseline hematologic values. At lower doses, the effects on hematopoiesis are much less pronounced suggesting that a modicum of residual LSD1 activity is sufficient to support blood cell formation. Thus, both the duration of LSD1 inhibition as well as the degree of inhibition are critical to the pharmacodynamic effects on myeloid lineages.

The intended dosing plan for ET patients is predicated on the observation that inhibition of LSD1 has a therapeutic effect when LSD1 is inhibited for a fraction of the 24-hour dosing cycle. The concentrations of IMG-7289 needed to achieve maximal effects on growth, differentiation, and apoptosis in vitro with primary

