### 6.5.3 Stopping Rules

IMG-7289 will be discontinued in the event of the following:

- Post DLT, the Investigator deems it unsafe for the patient to continue on IMG-7289.
- Post dose reduction due to DLT, the patient either worsens at any time or fails to demonstrate significant improvement within 14 days.
- Post temporary interruption of IMG-7289 due to platelet counts below  $50 \times 10^9/L$  (50,000/ $\mu L$ ), the patient's platelet counts don't return to  $> 150 \times 10^9/L$  (150,000/ $\mu L$ ) within 21 days.
- Any Grade 4 non-hematologic adverse event with failure to recover to Grade 3 within 7 days of drug cessation.

Patients who discontinue IMG-7289 will enter follow-up assessments beginning with EoT visit.

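### Table 1 holds dosing at hemoglobin below 8.5 g/dL but restarts it at 8 g/dL or above, so a value of 8.0 to 8.4 with platelets of at least 100 meets both rules

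*Combined protocol and SAP*

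**What the plan says.** The titration table appears twice with the same thresholds: as Table 1 in Section 6.2, and in the synopsis under IMG-7289 dosing. Its last row lists platelets <50 and Hb <8.5 g/dL as the condition for holding the dose. The re-challenge cell of that row reads "At 50% of prior dose when: - platelets return to" >=100, followed by Hb returning to >=8. The footnotes add:

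- "Re-challenge at 50% of the previous mg/kg dose".
- "Upon re-challenge, all of the above rules reapply".
- On the Hb >=8 entry: "PRBC transfusions allowed if at 0.15 mg/kg/d down-titrated dose level transfusions requirement remains stable within 2 units per month", with a further cap of 4 units per 28 days and a requirement for evidence of clinical benefit.

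The row above covers Hb 8.5 to <10 at any platelet count and lowers the dose by 0.15 mg/kg/d. During a hold, counts are checked at least weekly so that treatment can resume once they have recovered, if that is safe (Section 6.5.4). Section 6.3 carries the same table into the Additional Treatment Period, which can repeat.

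**The concern.** A restart threshold normally sits at or above the hold threshold, so that a patient must improve before dosing resumes. Here the Hb restart level is 0.5 g/dL below the hold level. A patient with adequate platelets held at Hb 8.2 already satisfies the Hb restart condition on the count that triggered the hold.

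This is an operative safety rule. Two members of staff could read the same result, one withholding the drug and the other giving it at half dose, and both could cite Table 1. Adherence in that range cannot be audited consistently. The plan expects effective doses to lower hemoglobin (Section 6.5.1), so the anemia rows are not purely theoretical.

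**Working it through.** There is no sample-size or error-rate figure to reproduce. The check is whether the rows of Table 1 are mutually consistent.

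**Inputs (Table 1, same in the synopsis).** Hold: platelets <50, Hb <8.5. Re-challenge: platelets >=100, Hb >=8, at 50% of the prior dose. Down-titrate by 0.15 mg/kg/d: Hb 8.5 to <10. The three other rows require Hb >=10, with platelets >400, 200 to 400, or 50 to 199.

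**Step 1: the hold row read as *or*.** Hold applies if platelets <50 or Hb <8.5. Re-challenge applies if platelets >=100 and Hb >=8. Both apply when platelets >=100 and 8.0 <= Hb <8.5. Width: 8.5 - 8.0 = 0.5 g/dL. Assuming Hb is reported to 0.1 g/dL, the values are 8.0, 8.1, 8.2, 8.3 and 8.4. Examples are platelets 120 with Hb 8.2, and platelets 300 with Hb 8.2.

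**Step 2: the hold row read as *and*.** Hold then needs both low platelets and low Hb, and no value meets both hold and re-challenge. But parts of the table become empty. On a grid of Hb 6.0 to 13.9 in steps of 0.1 (80 values) and platelets 20 to 795 in steps of 5 (156 values), the cells with no rule are:

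- Hb <8.5 with platelets >=50: 25 x 150 = 3,750
- Hb >=10 with platelets <50: 40 x 6 = 240
- Total: 3,990 of 80 x 156 = 12,480

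These include platelets 300 with Hb 7.0, platelets 30 with Hb 11, and platelets 120 with Hb 8.2. Under *or*, every cell has a rule. The cell count depends on the grid and is not a share of patients.

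**Step 3: which reading is better supported.** The other rows that give both counts are conjunctive, so the row is open as written. Section 6.5.3, however, describes "Post temporary interruption of IMG-7289 due to platelet counts below" 50 x10^9/L without mentioning hemoglobin, which implies that a low platelet count alone triggers a hold. That favors *or*, as does the absence of any rule for severe anemia under *and*.

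**Step 4: what follows from the overlap.** Take platelets 120 and Hb 8.2. The hold rule applies, the restart conditions are met, dosing resumes at 50%, all rules apply again, and an unchanged Hb triggers another hold. As a worst-case illustration from the 0.6 mg/kg/d starting dose: 0.6 x 0.5 = 0.3 mg/kg/d after one pass and 0.3 x 0.5 = 0.15 after two. For 70 kg that is 42, 21 and 10.5 mg. Recovering dose is slow: 0.2 mg/kg/d per step, no sooner than 4 weeks after the last titration, and only with platelets >400 and Hb >=10.

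**Step 5: after the change.** With re-challenge at Hb >=8.5 and the hold row written as *or*, no value on the grid meets both hold and re-challenge, and every cell still has a rule.

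**The case against.** The strongest reply is that a decision-maker exists. This is a single-site trial of up to 20 patients. The text under Table 1 sends clinically significant hematologic changes to the PI, Section 6.5.2 repeats this, and the synopsis and Section 11 add discussion with the manufacturer's medical staff. Re-challenge is also conditional on being safe. This stands in part: the gap is a missing default threshold, not unmanaged dosing. But none of these passages says whether 8 or 8.5 governs. The PI's stated freedom to depart from the table is worded for up- and down-titrations and names neither hold nor re-challenge. The transfusion footnote changes neither threshold and does not say that dosing may continue below 8.5.

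A second reply is that repeated halving is a worst case. This is correct. It needs Hb to stay at 8.0 to 8.4 after the dose is halved, although the plan describes the blood-count effects as dose-dependent and reversible, and transfusion is allowed within limits. A patient whose Hb fell through the 8.5 to <10 row may also have had a 0.15 mg/kg/d reduction already. Down-titration below Hb 10 should make values below 8.5 less common.

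A reader might also infer that the platelet rules conflict, because Table 1 restarts at >=100 while the stopping rule discontinues the drug if "the patient's platelet counts don't return to" >150 within 21 days. The documents do not support calling this a contradiction. The first rule permits a half-dose restart; the second tests whether recovery continues. They can be followed in sequence, and at day 21 the stopping rule governs. The plan also expects platelets to recover quickly off drug: "Recovery of peripheral counts is reversible, rapid, and temporarily overshoots baseline hematologic values", and "Cessation of IMG-7289 is invariably associated with a rebound in thrombopoiesis and platelet counts may easily exceed the baseline value". Loosening that stopping rule would be a clinical trade-off for which the documents give no basis.

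**Conclusion.** Wrong as written, in both copies of the table. Under the better-supported *or* reading, Hb 8.0 to 8.4 with platelets >=100 meets the hold and restart rules at once, over a range of 0.5 g/dL, and no text resolves it. Under the *and* reading the same row instead leaves severe anemia with adequate platelets without a rule. The row needs correcting on either reading.

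The conclusion rests on the table's thresholds and, for the overlap, on the *or* reading; the count of five values assumes reporting to 0.1 g/dL. The documents give no frequency for Hb below 8.5, so none is estimated. A reader might infer an effect on the Week 24 response rate; nothing in the documents shows one.

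**What to change.** In Table 1 and the synopsis copy:

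- Hold row: platelets <50 OR Hb <8.5.
- Re-challenge: platelets >=100 AND Hb >=8.5, at 50% of the prior dose.
- Keep the transfusion footnote consistent, for example by stating whether a transfused Hb counts towards the re-challenge level.
- Add that a hold takes precedence over the 0.15 mg/kg/d down-titration, since a case such as platelets 40 with Hb 9.0 falls in both rows once *or* is explicit.

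This is the conservative direction. Lowering the hold threshold to Hb <8 would also remove the overlap, but it would permit dosing where the plan now holds. It would also leave 8.0 to 8.4 without a rule unless the down-titration row were extended. That is a substantive safety change, not a clarification.

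The cost is an amendment to two tables and their footnotes, reported to the DSMB as Section 11 requires for protocol modifications. No visits, samples or patients are added, because counts during a hold are already at least weekly. The downside is small: some patients held for anemia would restart slightly later.
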